In summary, there is no current effective approach to prevent GDM-related fetal overgrowth. We demonstrated that choline sufficiency was critical for restoring normal placental transport and preventing fetal overgrowth in GDM mice. If similar effects of choline could be validated in humans, the practical impact would be remarkable because currently less than 10% of pregnant women in the U.S. consume the recommended 450 mg/d Adequate Intake of choline (47). Choline is readily available in common foods such as eggs, beans, and meat and is easy and safe to provide via a choline-rich diet or choline supplements. When used in clinical trials, choline supplementation was well tolerated and was not associated with any serious adverse events.

STUDY OBJECTIVES

Specific Aim 1: Determine the effect of MCS during pregnancy on birth weight in GDM.

Specific Aim 2: Determine the influence of MCS on macronutrient transport and epigenetic modifications in the placenta and cord blood.

HYPOTHESIS

Aim 1: We hypothesize that the choline group would have lower birth weight and fewer LGA neonates than the non- choline group.

Aim 2: We hypothesize that the choline group would reduce placental transport and increase DNA methylation of metabolic genes.

STUDY DESIGN

Subjects: A convenient sampling methodology will be adopted. We will recruit pregnant women diagnosed with GDM during the second trimester of pregnancy on a rolling basis. Block randomization will be conducted based on treatment methods (i.e. insulin therapy, oral hypoglycemics, or diet only) to randomly assign participants to the intervention and control groups. Recruitment will be conducted using the following methods: (i) study flyers will be posted

at the prenatal clinic; (ii) the principle investigator and her fellows will identify pregnant women who are potentially eligible by reviewing medical records. All these patients are routinely seen by members of the MFM team fellows. The PI or co-I will introduce the study to potential participants.

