Eligibility Criteria: The inclusion criteria include GDM pregnant women before gestational week 28. GDM is diagnosed with the 2-step process: blood glucose higher than the 140 mg/dL cut-off value after 50 g non-fasting 1-hr and 100 g 3-hr oral glucose challenges. Pregnant women are qualified to participate if they are English- or Spanish- speaking, over 18 years of age, having singleton pregnancy, intending to deliver their babies at Maimonides and are without any of the conditions listed in the exclusion criteria. Exclusion criteria include pre-existing hyperglycemia, diabetes, cardiovascular conditions and liver disease prior to pregnancy. Patients may choose to participate in the study and not donate a biopsy of their placenta or umbilical cord. Patients who desire stem cell donation or storage will not be able to donate a biopsy of their placenta or umbilical cord. These patients will not be excluded from the primary analysis.

Design and Data Collection Procedures:

All interaction with participants will occur at Maimonides while sample analyses will occur at Brooklyn College (where the co-I's lab is located). The PI or co-I will obtain written informed consent from the pregnant women before study entry. Randomization will be done by pharmacy after patient signs consent. It will be block randomization of 10 patients. After randomization, the PI or co-I will provide the participant in the intervention group with choline supplement pills containing 500 mg of choline bitartrate (235 mg choline, Douglas Lab). The participant will consume 2 pills per day to obtain 470 mg choline for 8 weeks. The recommended intake of choline in the form of Adequate Intake (AI) is 450 mg/d for pregnant women and the Tolerable Upper Intake Level (UL) is 3500 mg/d. Since less than 10% pregnant women reach the AI of choline intake and the upper quartile of choline intake is below 900 mg/d (48). The dosage we provide plus the habitual intake of choline in these pregnant women will fall between the AI and UL, i.e. sufficient but not exceeding the limit. The participants in the control group will receive a placebo that contains corn oil. Both groups will also receive standard prenatal multivitamins and 200 mg/d DHA provided by the study group. We will provide the participants with 5 weeks supply of supplements and we will verify their compliance during the time with daily check-off logs of supplement consumption and leftover pill count during their next visit.

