Anthropometric measurements and blood collection: We will measure the participants' weight and height using a medical weighing scale with mechanical height rods during the visits. To minimize food-related concentration differences in plasma biomarkers, participants will be instructed not to consume food for at least 4 hours before their blood draw in the morning. This is a standard recommendation for prenatal visits and is considered as safe (52, 53). We will also have preventative measures such as an examination bed to rest in and juices, food, and water should the women need them. About 20 mL of fasting venous blood will be drawn from each participant during the visits by a fellow/resident/nurse. Blood samples will be collected into one EDTA blood collection tube and one serum separator tube and centrifuged to obtain plasma, buffy coat, and serum. Samples will be processed and stored at -80°C at Brooklyn College until being used for analytical measurements.

Blood glucose management: We will obtain information about fasting glucose, hemoglobin A1C, medication and insulin therapy from medical charts of the participants.

Birth information and sample collection at delivery: The participants will notify the PI or co-I when they are admitted to the birth center by phone. We will also send them reminders as their due dates are approaching. In addition, **the birth center medical staff will be given a list of participant names, thus they will also contact the PI or co-I if a participant checks in when none of the study staff is on site.** The research team will be available 24/7. Once the baby is delivered, we will collect two tubes of cord blood to retrieve serum, plasma, and buffy coat. We will measure the size and weight of the placenta and process the placenta using the following method: full-thickness placental biopsies will be obtained using a 6-mm Keyes punch and stabilized in RNeasy[®] (for RNA), or frozen in liquid nitrogen (for other purposes). Samples will be transported to the co-I's lab for long-term storage at -80C before use.

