Sample Size: We anticipate a 10% dropout rate due to reasons such as participants moving out of the city, pre-term deliveries, or missed placental collection. Therefore, we expect to have at least 27 sets of complete data in each group. A statistical power analysis was performed for sample size estimation accounting for rates of dropout and missing data, based on data from a randomized controlled trial of choline supplementation which demonstrates that 2 x recommended intake of choline for 12 weeks is sufficient to increase plasma choline and alter placental global DNA methylation. The initial sample size of n=30/ group will allow detection of a >20% difference in birth weight, plasma choline and placental DNA methylation at $\alpha < 0.05$ and power = 80%.

Expected Outcomes: The successful completion of this study will provide valuable insights into the use of choline supplement as a modifier of placental macronutrient homeostasis in GDM to improve fetal growth outcomes.

Timetable:

	Quarter 1	Quarter 2	Quarter 3	Quarter 4
Participant Recruitment	n = 20	n = 20	n = 20	
Sample and Data Collection				
Choline measurements		Aim 1	Aim 1	Aim 1
Gene expression and epigenetic measurements		Aim 2	Aim 2	Aim 2
Data analysis				Both Aims
Result dissemination				Both Aims

We expect to complete recruitment by the end of the third quarter and complete dietary record, clinical information, and biosample collection in the middle of the fourth quarter. We will start analytical measurements once we obtain at least a third of the samples. We expect to complete analytical measurements by the end of the year. We will analyze and disseminate data in the last quarter.

Data Safety Committee Team Plans:

Randomization is a block randomization of 5 patients. After every block of randomization, the research team with a pharmacist and at least one external physician outside of the research team [[name]] will analyze the data to ensure that there are no unanticipated adverse effects via ultrasound fetal growth patterns. If unanticipated effects are found, we will report to IRB as per policy.

REFERENCES

1. Ferrara A. Increasing prevalence of gestational diabetes mellitus: a public health perspective. *Diabetes Care*. 2007;30 Suppl 2:S141-6. doi: 10.2337/dc07-s206. PubMed PMID: 17596462.

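### Investigators who obtain consent also supply the product by arm, and the research team reviews data after every block, yet no matching placebo, coded supply, code-holder or masked assessor is described

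*Combined protocol and SAP*

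**What the plan says.** Under Design and Data Collection Procedures, the PI or co-I obtains consent, and then "Randomization will be done by pharmacy after patient signs consent". The next step is that "the PI or co-I will provide the participant in the intervention group with choline supplement pills", with the active product identified by content and maker. For controls, "The participants in the control group will receive a placebo that contains corn oil". The text does not say who hands over the placebo, how many placebo pills are taken, or whether they look like the choline pills. The study team sees the product again at follow-up: "we will verify their compliance during the time with daily check-off logs of supplement consumption and leftover pill count".

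Under Subjects, the PI and the PI's fellows screen medical records, the PI or co-I introduces the study, and "All these patients are routinely seen by members of the MFM team fellows".

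Under Birth information and sample collection at delivery, "The participants will notify the PI or co-I when they are admitted to the birth center by phone". The study team collects cord blood and takes placental biopsies, and "We will measure the size and weight of the placenta". Samples then go to the co-I's laboratory, where western blotting is described as routine work (Analyses of macronutrient transport markers).

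Under Data Safety Committee Team Plans, data on fetal growth by ultrasound are analysed after each block by "the research team with a pharmacist and at least one external physician outside of the research team".

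**The concern.** A placebo protects a trial only if the people who enrol, handle specimens and read assays do not know who received it. Here the written dispensing step is organised by arm and given to investigators who recruit, and the surrounding team later produces outcomes. No step is described that would keep the arm from them.

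Two things are at stake. The first is enrolment: someone who sees past assignments and knows the block size can partly predict the next one, and in this plan the same roles approach and consent women. The second is measurement. Placental weighing, choice of biopsy site, sample handling and blot reading all involve judgement, and they feed Aim 2 directly. Restricting the block review matters for the same reason: a team that sees accumulating results by arm learns about the effect while it is still enrolling and measuring.

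**Working it through.** The plan gives no figure on masking, so there is none to reproduce. The check sets the sections side by side.

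**1. Who touches what**

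| Step | Who, per the plan | Section | Stated protection |
|---|---|---|---|
| Approach and consent | PI or co-I | Subjects; Design and Data Collection Procedures | None stated |
| Randomisation | Pharmacy | Design and Data Collection Procedures | Separate from the investigators |
| Supply of choline | PI or co-I, to a named arm | Same | None stated |
| Supply of placebo | Not stated | Same | None stated |
| Pill count | Study team | Same | None stated |
| Placenta and cord blood | Study team | Birth information and sample collection at delivery | None stated |
| Newborn weight | Not stated | – | – |
| PCR and blots | Co-I's laboratory side | Analyses of macronutrient transport markers | Triplicates; primer and antibody testing |
| Methylation | MassArray system available at a fee-for-service core | Epigenetic regulation of growth and metabolism | None stated on masking |
| Block review | Research team, pharmacist, external physician | Data Safety Committee Team Plans | Outside members present; not stated whether pooled or by arm |

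Masking needs a matching product, coded containers, someone who holds the code, and named masked roles. None of the four appears in the text. The only separation is pharmacy randomisation, and the next step names the arm.

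**2. Timing**

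The Timetable has recruitment running through Quarter 3 (20 + 20 + 20 = 60). Choline measurements and Aim 2 assays both start in Quarter 2, and laboratory work begins once a third of the samples are in. The Sample Size section expects supplementation to raise plasma choline. Maternal choline and betaine results could therefore suggest the arm while women are still being enrolled and Aim 2 assays are still being read. Coding the containers alone would not prevent this.

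**3. What seeing the arm would mean for enrolment**

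This is an illustration under assumptions: 1:1 permuted blocks of 10 (m = 5 per arm), and a recruiter who knows the block size, sees every earlier assignment in the block, and guesses the arm with more places left.

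- Assignments known with certainty in advance: 2m/(m + 1) = 10/6 = 1.67 of 10.
- Expected correct guesses: m + ½ × [2^(2m)/C(2m, m) − 1] = 5 + ½ × (1024/252 − 1) = 5 + 1.53 = 6.53 of 10, against 5 by chance.

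This measures predictability, not bias. Bias would also require the recruiter to act on the guess.

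**4. How often the review occurs**

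The block size is 10 under Design and Data Collection Procedures and 5 under Data Safety Committee Team Plans. If every block fills, that means 60/10 = 6 or 60/5 = 12 reviews. A block of 5 cannot be split equally between two arms. The two sections must be reconciled, because the block size sets both the number of looks and the predictability above.

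**The case against.** The strongest reply is that the text says what each group gets and who hands it over, not that this person knows the arm. Describing supply by group is ordinary protocol shorthand, and pharmacy randomisation leaves room for coded supplies. Every placebo differs from the active product in composition, so corn oil shows nothing about appearance. The Study design figure is not visible and may carry masking information. All of this stands: knowledge of the arm is an inference, and the plan calls itself neither open nor blinded.

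Some stronger readings are therefore tempting but not supported:

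- *The investigators know the arm throughout, so the placebo is defeated.* The documents are silent on coding; they do not rule it out.
- *The block review unmasks the team.* It is described as a check for unanticipated adverse effects, with a pharmacist and an external physician present. It is not said to be by arm, and a pooled review would not disclose assignments.
- *Birth weight is biased because unmasked staff weigh the newborn or choose when to deliver.* Nobody is named for either task. Glucose and insulin information is taken from charts, and routine care is attributed to the fellows. Any figure in grams would need outside inputs.
- *All Aim 2 results come from one unmasked laboratory.* Methylation is quantified on a system available at a fee-for-service core.

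The assay quality rules (isotope-labelled standards, duplicates with rerun limits, triplicates) also deserve credit. They control precision, however, and not the effect of knowing the arm.

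What the reply does not remove is that the written steps place supply by arm with the people who consent, and accumulating data with the research team, without any stated safeguard.

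**Conclusion.** The concern holds in this form: on a plain reading, the described dispensing and block review can reveal the arm to people who enrol later participants and who produce the placental, PCR and blot outcomes, and no section plans against it. This goes beyond a missing sentence on blinding, because two stated procedures would have to change or be qualified. It should be corrected, but it does not show that the placebo has failed.

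No size of bias can be computed from the documents. The only number offered, 6.53 against 5 correct guesses per block of 10, rests on 1:1 permuted blocks and a recruiter who sees each assignment. The conclusion also assumes that the missing figure contains no masking scheme. If coded supply and masked reading are already practice, writing them down closes the point.

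**What to change.** Amend the protocol as follows.

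- **Supply.** Pharmacy, which already randomises, issues both products in coded containers with the same pill count and, where feasible, the same appearance. Pharmacy holds the code. The PI or co-I hands over a numbered container, not an arm.
- **Samples and readings.** Specimens carry study numbers only. Placental measurement, PCR and blot reading are done without the arm.
- **Choline and betaine results.** Maternal values are withheld from enrolling staff and from those reading Aim 2 assays until those assays are locked.
- **Block review.** Any arm-level data go only to the pharmacist and the external physician already named. The research team sees pooled data.
- **Statement of roles.** Say who is masked, including whoever weighs the newborn, and reconcile the two block sizes.

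The cost is pharmacy labelling time, a protocol amendment, and over-encapsulation if the products do not match. At the plan's 2 pills a day for 8 weeks, with the same count in both arms, that is at most 60 × 2 × 56 = 6,720 units, which is not trivial for a small trial. If the products cannot be matched, the sample coding, the withholding of choline results and the restricted review still apply, and they require no change to the products.

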The participants will come in for a total of 3 visits at times of routine clinical care. The first visit will be at 28 weeks of gestation when we enroll the participants, the second visit will be at

32 weeks of gestation, and the third visit will be at 36 weeks. There are additional routine clinic visits (e.g., at 32 weeks) during which information can be obtained if a patient missed a study visit. We will collect a baseline questionnaire at the first visit (approximately 20 minutes), conduct 3-day dietary recalls after the first visit (approximately 20 minutes, each), and check current weight and collect 20 mL blood samples at all visits. At delivery, we will collect placenta samples and cord blood from the participants (**Figure 3**).

Baseline questionnaire: The questionnaire includes demographic and medical information such as age, due date, ethnicity, parity, marital status, education level, occupation, household income, medical insurance, substance use, medication use, nutrition supplement, family history of chronic diseases, and self-reported pre-pregnancy weight.

[figure not shown]

Figure 3. Study design

Dietary assessment: Three 24-hr dietary recalls, 2 on weekdays and 1 on a weekend day, will be obtained from each participant by a trained research assistant (RA) via phone calls following the first visits to quantify dietary choline intakes. The multi-pass method of Harnack and colleagues will be used (49). This method is widely used in dietary recall data collection for research (e.g. National Health and Nutrition Examination Survey) and **validated for its accuracy in assessing dietary intake (50)**. The RA will record food identification, quantity, ingredient specification, preparation method and enter data into the Nutrition Data System for Research (NDSR) software to analyze choline intake. The RA will also ask participants about their **physical activity (PA)** during the past 24 hours using the PA recall instrument (51).

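### Pills stop at about week 36 but birth weight, placenta and cord blood are obtained at delivery; dosing both arms to delivery would be a cheap improvement

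*Combined protocol and SAP*

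**What the plan says.** The Design and Data Collection Procedures section fixes both dose and duration: "The participant will consume 2 pills per day to obtain 470 mg choline for 8 weeks". It places the start at enrolment, "The first visit will be at 28 weeks of gestation when we enroll the participants", with a second visit at week 32, "and the third visit will be at 36 weeks". Supplements are handed out as a five-week supply and leftover pills are counted at the following visit. The number of issues is not stated, and no study visit follows week 36. Controls receive a corn oil placebo, whose duration is not given separately.

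The tissue samples come later. The same section says "At delivery, we will collect placenta samples and cord blood from the participants", and the paragraph on birth information and sample collection adds "Once the baby is delivered, we will collect two tubes of cord blood to retrieve serum, plasma, and buffy coat". Aim 1, under Study Objectives, is to "Determine the effect of MCS during pregnancy on birth weight in GDM"; the Data Analysis section compares birth weight and LGA between arms.

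No passage extends dosing beyond eight weeks or explains the stop. The Sample Size section relies on a trial in which choline was taken for 12 weeks.

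**The concern.** The planned exposure ends before the outcomes of both aims are obtained. This matters most for measures that describe the tissue at the moment of sampling: placental transporter mRNA and protein, and AKT/mTOR phosphorylation. Placental choline metabolites belong here too if they are measured; Data Analysis names them, but its measurement paragraph describes maternal plasma only. For birth weight and LGA, the last weeks of fetal growth before a term birth are untreated by plan. Maternal plasma choline at weeks 28, 32 and 36 is not affected.

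What is at stake is interpretation. If placental markers or birth weight do not differ between arms, the finding could mean that choline does nothing, or that the pills had stopped some weeks before. Nothing in the plan separates the two explanations.

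**Working it through.** **Inputs from the protocol**
- Two pills a day, 235 mg choline each, for 8 weeks; start at the 28-week visit; last study visit at week 36; five-week supply; upper limit 3,500 mg/d; upper quartile of habitual intake below 900 mg/d (all Design and Data Collection Procedures).
- Eligibility before week 28 (Eligibility Criteria).
- 30 women per group, and 12 weeks of supplementation in the cited trial (Sample Size).

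**Assumed:** births at 37 to 40 weeks. The Sample Size section lists pre-term delivery among the reasons for dropout, so complete data are expected mainly from term births, but no delivery week is given.

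**1. Daily dose.** 2 × 235 = 470 mg, which agrees with the plan.

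**2. End of course.** 28 + 8 = week 36.

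**3. Gap and exposure.** Gap = birth week − 36. Share = gap / (birth week − 28). Exposure if continued = birth week − 28.

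| Birth week | Gap | Share of enrolment-to-birth time | Exposure if continued | Change from 8 weeks |
|---|---|---|---|---|
| 37 | 1 wk (7 d) | 1/9 = 11.1% | 9 wk | +12.5% |
| 38 | 2 wk (14 d) | 2/10 = 20.0% | 10 wk | +25% |
| 39 | 3 wk (21 d) | 3/11 = 27.3% | 11 wk | +37.5% |
| 40 | 4 wk (28 d) | 4/12 = 33.3% | 12 wk | +50% |

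Births at or before week 36 have no gap.

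**4. Sensitivity to start week (assumed; births at 37 to 40).** Start at 26: gap 3 to 6 weeks. At 27: 2 to 5. At 28: 1 to 4. At 29: 0 to 3. At 30: 0 to 2.

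**5. Leftover pills.** If five-week supplies are issued at weeks 28 and 32 (an assumption), women hold 10 weeks of pills for an 8-week course, so 2 weeks (2 × 14 = 28 pills) could remain. If all were taken after week 36, the gap would shrink from 1 to 4 weeks to 0 to 2. That use would fall outside the written regimen, and no planned visit would count it.

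**6. Against the cited trial.** 8/12 = 67% of its duration. Dosing to delivery gives 9 to 12 weeks and matches 12 for a birth at week 40.

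**7. Margin to the upper limit.** 900 + 470 = 1,370 mg/d; 1,370/3,500 = 39%. The 900 is a bound on the upper quartile, not a maximum. The daily dose does not change, so neither does the margin.

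**8. Intake correlation in Data Analysis.** With dosing to delivery, cumulative supplement is 470 × 63 days = 29,610 mg for a birth at week 37 and 470 × 84 days = 39,480 mg at week 40, a third more (12/9 = 1.33). Cumulative dose would rise with gestational age at birth, which also drives birth weight. Average daily supplement would be 470 mg in both cases.

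**The case against.** The strongest reply is that this is a design preference. A fixed eight-week course gives a valid randomised estimate of the effect of an eight-week course. It is uniform across women, and it ends at a visit where blood is drawn and pills can be counted. A course in weeks 28 to 36 is also during pregnancy, so Aim 1 is not contradicted. All of this stands, and it is why the point is an improvement and not an error.

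Three stronger readings are tempting, and the documents support none of them.
- A reader might infer that the effect fades after the last pill, that methylation reverts, or that eight weeks is too short. No passage gives a duration-response or a washout. The 12-week trial shows that 12 weeks sufficed, not that 8 would fail.
- A reader might infer lost power. That needs an effect proportional to weeks covered, which the documents neither support nor refute, and they give no SD behind the sample size.
- A reader might average the supplement from week 28 to birth (for a birth at week 40, 470 × 8/12 = 313 mg/d) and call it a shortfall. The plan promises 470 mg/d for eight weeks, not an average to birth.

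The objection is also right that dosing to delivery makes exposure depend on delivery date, and that compliance after week 36 is harder to verify. These are real costs of the change.

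**Conclusion.** The point holds as a cheap improvement. As written, pills stop at about week 36 while birth weight, LGA, placenta and cord blood are obtained at delivery, and no reason is given. For births at 37 to 40 weeks the planned gap is 1 to 4 weeks. Starting before week 28 lengthens it; a later start or use of leftover pills would shorten it.

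This rests on the assumed delivery weeks and on the text alone, because the study design figure (Figure 3) is not shown and might carry a dosing window. The size of any lost effect cannot be computed from the documents. Dosing to delivery removes one rival explanation for a null result; it does not by itself justify the 20% difference used for sizing. Confidence is medium.

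**What to change.** - In both arms, replace the fixed eight-week duration with dosing from the 28-week visit until delivery, at the same daily dose. State whether the study's multivitamins and DHA continue as well.
- At the existing 36-week visit, dispense enough to reach week 41: up to a further five-week supply (5 × 7 × 2 = 70 pills), less any left over. With 28 left, 42 would do.
- Collect the log and leftover pills at delivery and record the date of the last pill. The contacts already exist: "The participants will notify the PI or co-I when they are admitted to the birth center by phone", and "We will also send them reminders as their due dates are approaching". Add the request to that reminder.
- Compare arms as randomised, whatever the length of exposure.
- In the correlation of choline intake with birth weight, use average daily intake, not cumulative intake.

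**Cost.** An amendment and consent wording; at most 70 × 60 = 4,200 pills, active plus placebo, of which 14 to 56 per woman would be taken for births at 37 to 40 weeks; and a small added task at delivery, sometimes when no study staff are on site. No new visit or sample is needed. Exposure would vary from 9 to 12 weeks with delivery date, and compliance after week 36 would be checked less reliably. The documents give no pill price.

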Data Analysis: *Specific Aim 1: Determine the effect of maternal choline supplementation (MCS) during pregnancy on birth weight in GDM.* To achieve this aim, we will compare the birth weight as well as incidence of LGA between the intervention versus control group. We will also assess the influence of MCS on blood and placenta choline metabolite status, as well as the correlation between total choline intake (diet + supplement) or choline metabolite status and birth weight.

Dietary intake assessment: As mentioned above, dietary intake data collected from 3-day dietary recalls will be analyzed by the NDSR software (54, 55). Daily intakes of total choline will be calculated by multiplying the frequency of consumption by the sum of choline derivatives including free choline, phosphatidylcholine (PC), glycerophosphocholine (GPC), phosphocholine, and sphingomyelin of each food item(56). Daily intakes of betaine (the oxidation product of choline) will be calculated by multiplying consumption frequency and

betaine content of each food. Average daily intakes will be calculated as the average daily consumption of total choline and betaine over the 3 days of dietary recalls.

Measurements of choline metabolites: Free choline, betaine and other choline derivatives [e.g. PC, GPC, lysophosphatidylcholine, dimethylglycine, trimethylamine oxide (TMAO)] will be measured in maternal plasma using liquid chromatography (LC)-mass spectrometry (MS) /MS (57, 58) as was conducted in previous studies. **To ensure the accuracy and reproducibility of data**, stable isotope labeled standards will be used in extraction, all samples will be quantified based on a 6-point standard curve, and each sample will be run in duplicate. Samples with a coefficient of variation (CV) % higher than 5% within run or 10% between run will be rerun.

Specific Aim 2: Determine the influence of MCS on macronutrient transport and epigenetic modifications in the placenta and cord blood. To achieve this aim, we will determine expression of fat and glucose transporters, as well as the upstream regulating pathways AKT/mTOR in placental biopsies from the participants. We will measure the site-specific DNA methylation of key growth and metabolism related genes in the placenta and cord blood.

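### The birth-weight comparison in Aim 1 gives no role to treatment method, the stated basis of randomisation, or to baseline data, so an ordinary t-test would be valid but may be conservative

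*Combined protocol and SAP*

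**What the plan says.** Data Analysis, Specific Aim 1, gives the whole plan for the between-arm comparison in one sentence: "To achieve this aim, we will compare the birth weight as well as incidence of LGA between the intervention versus control group". No other section adds a test, a model, an effect measure or a covariate. For choline status the same section says: "We will also assess the influence of MCS on blood and placenta choline metabolite status". It gives no role there to the value at entry.

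Study Design (Subjects) describes allocation: "Block randomization will be conducted based on treatment methods (i.e. insulin therapy, oral hypoglycemics, or diet only". Design and Data Collection Procedures gives blocks of 10 and the Data Safety Committee Team Plans give blocks of 5. Neither mentions strata.

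The baseline questionnaire records "age, due date, ethnicity, parity, marital status" and, further on, "family history of chronic diseases, and self-reported pre-pregnancy weight". Height and weight are measured at the visits, and blood is drawn at all three, the first at 28 weeks.

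Sample Size states: "The initial sample size of n=30/ group will allow detection of a >20% difference in birth weight, plasma choline and placental DNA methylation", at 80% power. It also states: "Therefore, we expect to have at least 27 sets of complete data in each group". It gives no SD for birth weight.

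**The concern.** When allocation is balanced within levels of a factor that predicts the outcome, the arm difference varies less from trial to trial than an ordinary two-sample t-test assumes. The t-test leaves the between-stratum variation in its error term. Its standard error is then too large, its confidence interval too wide and its true type I error below the nominal level. A model containing the factor removes this.

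Baseline variables that were not used in allocation can also narrow the interval if they predict birth weight. The trial already schedules several of them. With about 30 women per arm, precision is scarce. Leaving the model open also means that covariates could be chosen after the data are seen.

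**Working it through.** **The plan's own figures.** The dropout arithmetic reproduces: 30 × 0.90 = 27. The power statement cannot be checked without an SD. By the noncentral t (two-sided 0.05, 80% power), the detectable difference is 0.777 SD at 27 per group and 0.736 SD at 30. A 20% difference sits at that limit only if the CV is 20/0.777 = 25.7% or 20/0.736 = 27.2%. At an assumed CV of 20%, unadjusted power for a 20% difference is already 0.950 (27) or 0.968 (30).

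**Number analysed.** Losses counted in reaching 27 include missed placental collections. Eligibility Criteria says of women who give no biopsy: "These patients will not be excluded from the primary analysis". The number with a birth weight may therefore lie between 27 and 30 per group.

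**Treatment method, allocation stratified.** Let R² be the share of birth-weight variance explained by treatment method (assumed). With balance within strata, the variance of the arm difference is (1 − R²)·2/n. The t-test estimates roughly 2/n, so its SE is too large by 1/√(1 − R²): 1.054 at R² = 0.10 and 1.118 at 0.20. With n = 27 and df = 52 the critical value is 2.007, so the effective critical values are:
- R² = 0.10: 2.007 × 1.054 = 2.115, a type I error of about 3.9%
- R² = 0.20: 2.007 × 1.118 = 2.244, a type I error of about 2.9%

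The adjusted test has df = 50 and noncentrality 0.75·√13.5/√(1 − R²) at a true difference of 0.75 SD. This is 2.905 and 3.081, giving power of 81% and 86%.

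Simulation of 54 women in exactly balanced strata of 28/14/12 (assumed sizes; 400,000 trials per cell):

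| Stratum R² | Type I, unadjusted | Type I, adjusted | Power at 0.75 SD, unadjusted | Power, adjusted |
|---|---|---|---|---|
| 0 | 5.0% | 5.0% | 77.2% | 77.2% |
| 0.10 | 3.9% | 5.0% | 78.2% | 81.3% |
| 0.20 | 2.8% | 5.0% | 79.5% | 85.7% |

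A shorter run gave unadjusted type I error of 3.8% and 2.6%, with power of 77% and 79% against 80% and 86% adjusted. The difference is simulation error.

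**Cost if treatment method predicts nothing.** Two degrees of freedom are lost. The critical value moves from 2.007 to 2.009, and power at 0.777 SD from 0.800 to 0.799.

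**Four terms, all balanced only by chance** (two for treatment method, plus BMI and parity). The variance factor is (1 − R²)(1 + q/(2n − q − 3)) with q = 4. At n = 27 this is (1 − R²)(1 + 4/47) = 1.085(1 − R²); at n = 30 it is (1 − R²)(1 + 4/53) = 1.075(1 − R²).

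| Total R² (assumed) | Detectable difference, n = 27 | 95% CI half-width, n = 27 | Detectable difference, n = 30 |
|---|---|---|---|
| unadjusted | 0.777 SD | 0.546 SD | 0.736 SD |
| 0 | 0.811 | 0.570 | 0.764 |
| 0.10 | 0.769 | 0.541 | 0.725 |
| 0.20 | 0.725 | 0.510 | 0.683 |
| 0.30 | 0.678 | 0.477 | 0.639 |
| 0.40 | 0.628 | 0.442 | 0.592 |

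Break-even R² is 0.081 (27) or 0.073 (30). At R² = 0, 80% power falls to 0.766 or 0.770. Under stratified allocation only BMI and parity carry the imbalance penalty, so at n = 27 the factor is about 1 + 2/47 = 1.043 rather than 1.085.

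**Plasma choline.** The ANCOVA SE relative to using the follow-up value alone is √[(1 − r²)(1 + 1/50)] at n = 27. For an assumed correlation r with the entry value of 0.3, 0.5 or 0.7 this is 0.963, 0.875 or 0.721.

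**The case against.** The plan says compare. It does not say t-test or unadjusted, so adjustment is unplanned rather than excluded, and every loss above is measured against a test the plan never names. R², SD, stratum shares and the entry correlation are all assumed. At an assumed CV of 20% or less there is little power left to recover for a 20% difference. All of this stands. It limits the size of the point but leaves the gap: no section says whether the randomisation factor enters the analysis.

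Three stronger readings are tempting, and the documents do not support them.
- A reader might infer that an unadjusted comparison would be biased or invalid. Allocation is random, so it would be neither. Under stratification it errs on the conservative side.
- A reader might infer that the baseline data go wholly unused. Aim 1 does correlate choline intake and metabolite status with birth weight. The omission concerns the arm comparison only.
- A reader might take 0.07–0.08 as the general threshold for adjustment to pay. It holds only if all four terms are balanced by chance. For treatment method under stratified allocation there is almost no threshold to clear.

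Two further objections also stand. Choosing BMI and parity over other recorded variables is a judgement. And the text does not show that the 28-week blood sample precedes the first dose: it places randomisation after consent and the first sample at the enrolment visit, without giving their order.

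**Conclusion.** The point holds as one of efficiency and prespecification. If allocation is stratified as Study Design says, an ordinary t-test would have a standard error about 5% or 12% too large at an assumed stratum R² of 0.10 or 0.20. It would give up about 3 or 6 power points at 0.75 SD. Those figures assume near-exact balance within strata; incomplete blocks and losses would blur it. If allocation is not stratified, the t-test holds its nominal level and only the conditional precision argument remains.

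The gain from BMI and parity is unknown and could be slightly negative. At a CV of 20% or less, the benefit is mainly a narrower interval for differences below 20%.

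**What to change.** 1. Reconcile Study Design, Design and Data Collection Procedures, and the Data Safety Committee Team Plans on whether allocation is stratified and on block size (10 or 5; an odd block cannot split equally between two arms).
2. Prespecify a linear model of birth weight on arm and treatment method as recorded at randomisation (three levels), plus a small named set of pre-randomisation covariates such as pre-pregnancy BMI (self-reported weight, measured height) and parity.
3. Report the adjusted difference with its 95% CI, and the unadjusted difference as a sensitivity analysis.
4. Use no post-randomisation covariates, such as later treatment changes or gestational age at delivery. Chart glucose and HbA1c carry no stated date, so they qualify only if dated before randomisation and named in advance.
5. Analyse plasma choline at 32 and 36 weeks by ANCOVA on the 28-week value, and state in the plan that this sample is drawn before the first dose. If it is not, drop that adjustment.

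The cost is SAP wording and a little programming, with no new data. If the covariates predict nothing, the treatment-method terms cost about 0.1 power point under stratified allocation, and all four terms about 3 points if balanced only by chance.
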